10.2. Secondary efficacy endpoints

All secondary efficacy endpoints will be analyzed and presented in full detail by means of descriptive statistics and inferential analyses as appropriate.

For CDASI, SF-36v2, TIS, and the individual CSMs the mean change from Baseline (Week 0) to the end of treatment will be presented by a full set of descriptive parameters: number of subjects with non-missing values, mean, standard deviation, median, minimum and maximum, 1st and 3rd quartile, 95% CI.

Moreover, for those continuous secondary endpoints, an analysis of covariance (ANCOVA) will be used to analyze changes from baseline to end of treatment (Week 32 or earlier end of treatment visit). The model will include treatment as a fixed factor. Center will be included as random factor. The baseline value of the variable to be analyzed will be included as a covariate. Least square means will be derived and presented together with 95%-confidence intervals by treatment group. Moreover, two-sided 95% confidence intervals will be derived for the overall difference in least square means between Octanorm and placebo treatment.

The time to clinically important deterioration will be analyzed by the product-limit method for the analysis of survival data, and presented as Kaplan-Meir plots alongside a Log-Rank test for differences between treatment groups.

The detailed list of all tables, figures and graphs, and the analysis populations used for each analysis will be provided in a separate document later, when all feedback from authorities will be available.

Property of Octapharma. Do not copy or distribute without written permission.

11. Safety and Tolerability Analyses

The safety analysis will comprise descriptive statistics, tabulations and listings of all treatment emergent adverse events (TEAEs), safety laboratory results, viral markers, vital signs, Wells' scores, Doppler scan results, and physical examination findings.

The safety analysis will be made with the SAF population. Patients will be analyzed by actual treatment, data tabulations will present the treatment arms and the total count in a side-by-side manner.

11.1. Adverse Events

All reported AEs will be coded according to MedDRA.

An AE is defined as treatment-emergent, if first onset or worsening is during the treatment period. Only treatment-emergent AEs (TEAEs) are accounted for in the analysis.

For each TEAE, the exact time of onset will be recorded. A TEAE will be classified as infusional AE if the onset is during the first infusion session of a given infusion cycle, between the two infusion sessions of the same cycle, or within 72 hours after the end of the 2nd infusion session of the same infusion cycle.

All reported events will be listed and tabulated in full detail; in particular the following key figures will be presented:

- Total incidence and number of TEAEs reported by severity and overall
- Incidence and number of related TEAEs by severity and overall
- Incidence and number of TEEs and HTRs
- Incidence and number of SAEs
- Incidence and number of TEAEs leading to withdrawal
- Incidence and number of infusional AEs by severity and overall
- Number of infusion cycles with infusional AEs

Narratives will be prepared describing each death, other SAEs, and other significant AEs that are judged to be of special interest because of clinical importance, including all TEEs and HTRs reported.

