## 9.9 Safety Analysis Plan

Evaluation of safety will be made with the SAF population. Patients will be analysed by actual treatment group.

If present, adverse events in patients who are not included in the SAF population will be listed.

The safety analysis will comprise descriptive statistics, tabulations and listings of all adverse events, safety laboratory results, viral markers, vital signs, physical examination findings, and any other relevant safety information as detailed in Section 7.3.

Adverse events will be coded according to the MedDRA system and described according to their preferred term and the system organ class. Statistical analysis will not take in account MedDRA low level terms but will start at preferred term level. Information pertaining to adverse events noted during the study will be listed by patient, detailing verbatim given by the investigator, preferred term, system organ class, date of onset, date of resolution, outcome, seriousness, criteria of seriousness, and relationship to study treatment. The onset of adverse events will also be shown relative (in number of days) to the day of first infusion of study treatment. All serious adverse events will be described in detail in the study report, based on CIOMS-listings and CRF-data.

In addition to an analysis of all adverse events, adverse events with a causal relation to the study treatment, that is adverse reactions, will be analysed separately.

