This phase III study is conducted to determine the efficacy of subcutaneous immunoglobulin *octanorm* in the maintenance treatment of patients with dermatomyositis (DM) who have previously responded to IGIV therapy. It is designed as parallel group, double-blind, randomized, multicenter study with up to 2 weeks for screening, followed by a 32-week treatment period and 1 week of safety follow-up.

Patients eligible after screening will be randomized 1:1 to receive infusion cycles of either *octanorm* 0.5 g/kg/week or placebo every week for 32 weeks. The weekly infusion will be performed in two separate sessions, either on the same day or on two consecutive days or with maximum one day in between two sessions.

The primary endpoint is defined as the occurrence of a clinically important deterioration during the treatment period. The safety follow-up will ensure a complete record on all safety assessments, including adverse events and changes in concomitant medications.

The structure and content of this SAP provides sufficient detail to meet the requirements identified by the FDA and International Conference on Harmonization (ICH) of Technical Requirements for Registration of Pharmaceuticals for Human Use: Guidance on Statistical Principles in Clinical Trials¹.

The following documents were reviewed in preparation of this SAP:

- Clinical Study Protocol SCGAM-02, Version 07, dated 16-Jul-2018

The reader of this SAP is encouraged to also read the clinical protocol for details on the planned conduct of this study. Operational aspects related to collection and timing of planned clinical assessments are not repeated in this SAP unless relevant for the specification of the planned analyses.

¹ International Conference on Harmonization. (1998). Guidance on Statistical Principles. ICH Topic E9 (Statistical Principles for Clinical Trials) (p. 37). London: International Conference on Harmonization.

2. Purpose

This SAP outlines the statistical analyses to be performed on data collected in study SCGAM-02, and the resulting output that will be compiled to support the completion of the Clinical Study Report (CSR).

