3.2.2. Secondary Target Variables

For Efficacy and Quality of Life (QoL), secondary endpoints will be based on:

- The modified Cutaneous Dermatomyositis Disease Area and Severity Index (CDASI): Mean change from baseline (Week 0, defined as end of IgIV therapy) to end of the treatment period (Week 32 or earlier drop-out visit)
- Six Myositis core set measures (CSMs) used for calculation of the Total Improvement Score (TIS), i.e. MMT-8, Physician's Global Disease Activity, Patient's Global Disease Activity, Extra-Muscular Disease Activity, Muscle enzymes, and Health Assessment Questionnaire (HAQ): Mean change from baseline to end the treatment period
- SF-36v2 Health Survey: Mean change from baseline to end the treatment period
- TIS: Mean change from baseline to end the treatment period
- Time to clinically important deterioration during the treatment period
- Number and type of deviations from protocol requirements relating to home treatment (dosing, timing)

For Safety, target variables will be:

Throughout the entire Period:

- Occurrence of all adverse events with particular emphasis on thromboembolic events (TEEs) and hemolytic transfusion reactions (HTRs)
- Local injection site reactions
- Vital signs (blood pressure, heart rate, body temperature and respiratory rate)
- Physical examination
- Laboratory parameters (hematology, clinical chemistry, urinalysis)

At Baseline and end of Treatment Period:

- Tests for viral safety
- Pregnancy test, if applicable

Property of Octapharma. Do not copy or distribute without written permission.

4. Study Methods

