8.3. Handling of Missing Data

In general, missing data will not be imputed, with a few exceptions. If a subject is prematurely withdrawn from the study, or misses data required for the evaluation of the primary endpoint, this subject will be analyzed as having a clinically important deterioration. For missing weight measurements the last available body weight will be used for all calculations related to dosing; in individual patient data listings such last observations carried forward (LOCF) will be tagged.

Missing data in other variables will not be replaced by any method of imputation; instead, the frequency of missing values will be presented.

No analyses of the patterns of missing data will be done.

For adverse events the following will be applied:

An Adverse Event (AE) is defined as treatment-emergent, if first onset or worsening is after start of the first infusion of *octanorm* or placebo.

If the start date and time of an AE are partially or completely missing, the AE will be assumed to be treatment-emergent if it cannot be definitely shown that the AE did not occur or worsen during the treatment emergent period (worst case approach). Missing dates and times will not be replaced.

For medications the following will be applied: A medication will be assumed to be concomitant if it cannot be definitely shown that the medication was not administered during the treatment period as defined in section 8.4 below. Missing dates will not be replaced.

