8.4. Derived and Computed Variables

The following derived and computed variables have been initially identified as important for the analysis of the primary and secondary target variables. It is expected that additional variables will be required. The SAP will not be amended for additional variables that are not related to the primary target or key secondary target variables. Any additional derived or computed variables will be identified and documented in the SAS programs that create the analysis files. If the SAP is not amended, further derivations related to primary and secondary target variables will be described in the CSR.

- **Age group:** For subgroup analyses related to age we initially plan for the following age groups: 18-39 years (young adults) / 40-65 years (middle-aged) / >65 years (elderly). In case the actual age distribution of the study population results in groups of very different sizes, these defining intervals might be adjusted in a subsequent SAP, but before the blind is broken.
- **Body Mass Index:** $BMI = (\text{Body weight}) / \text{Height}^2$ [Unit: kg/m²]
- The **treatment period** is defined as the period between the first treatment with study drug (*octanorm* or placebo) to the end of the observation period. This will usually be the termination visit (Week 32 or earlier in case a patient is discontinued from the study).
- **Clinically important Deterioration** is defined as
 - 1) MMT-8 worsening ≥ 6 points (scale of 150) OR CDASI worsening ≥ 5 points, AND
 - 2) A Physician's Global Disease Activity VAS worsening ≥ 2 cm.

9. Study Subjects and Demographics

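### The SAP defines treatment-emergent twice with different end points, so events dated between the termination visit and the Week 33 safety follow-up may be left out of the by-arm tables

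*SAP*

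**What the plan says.** Two definitions of treatment-emergent stand in the SAP.

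- **SAP 8.3** (missing data): an event is treatment-emergent "if first onset or worsening is after start of the first infusion of" either study product. No end is given.
- **SAP 11.1** (adverse events): an event is treatment-emergent "if first onset or worsening is during the treatment period. Only treatment-emergent AEs (TEAEs) are accounted for in the analysis".

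SAP 8.4 runs the treatment period from the first study treatment to the end of the observation period, and adds: "This will usually be the termination visit (Week 32 or earlier in case a patient is discontinued from the study"; the bracket closes there.

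Other text bears on the same window:

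- SAP 3.2.2 lists, for the whole study period, "Occurrence of all adverse events with particular emphasis on thromboembolic events (TEEs) and hemolytic transfusion reactions (HTRs".
- The SAP preface gives the purpose of the last visit: "The safety follow-up will ensure a complete record on all safety assessments, including adverse events and changes in concomitant medications".
- SAP 11 opens by promising "tabulations and listings of all treatment emergent adverse events (TEAEs", whereas Protocol 9.9 says "The safety analysis will comprise descriptive statistics, tabulations and listings of all adverse events".
- The key figures in SAP 11.1 include "Incidence and number of TEEs and HTRs", and narratives are planned for every reported TEE and HTR.
- Protocol 6.1.11 places the safety follow-up at Week 33, 1 to 2 weeks after the last infusion, with both Wells scores assessed in all patients.
- Protocol 7.3.5 has TEEs and HTRs reported as SAEs, and Protocol 7.3.9 takes SAEs up to 4 weeks after the last infusion.

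**The concern.** Two programmers working from different sections of the SAP could produce different adverse event, TEE/HTR and SAE tables from the same data. The difference falls on the follow-up week, which the plan includes in order to complete the safety record. TEEs and HTRs are the two adverse events of special interest, and counts are likely to be low enough for one event to be visible in the table.

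Taking SAP 8.3 as it stands is not a clean answer either. Patients who deteriorate may receive 2 g/kg IGIV after their termination visit (Protocol 4.3.1), and all patients go back to their earlier treatment or another standard of care (Protocol 4.6). With no end to the window and no flag, an event that follows another immunoglobulin product would be counted in the randomized arm without distinction.

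**Working it through.** **1. The plan's own figure.** The only planning figure used here is the arm size. Inputs from Protocol 9.1: 58% versus 27%, two-sided alpha 0.05, power 80%, Pearson chi-square. With mean proportion 0.425:

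n = [1.960 × √(2 × 0.425 × 0.575) + 0.842 × √(0.58 × 0.42 + 0.27 × 0.73)]² / 0.31² = 38.7, so 39 per arm. Power at 39 is 80.3%.

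The stated 39 is reproduced. Nothing in this point changes it.

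**2. The calendar.** Cycle k nominally starts in week k − 1.

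| Event | Day | Days after last cycle starts |
|---|---|---|
| Cycle 32 starts | 31 × 7 = 217 | 0 |
| Termination visit, Week 32 | 224 | 7 |
| Safety follow-up, Week 33 | 231 | 14 |
| End of SAE reporting, 4 weeks | 217 + 28 = 245 | 28 |

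Under 8.3, an event dated from day 225 to day 231 is treatment-emergent. Under 11.1 with 8.4 read naturally, it is not. The gap is 1/33 = 3.0% of the time from first infusion to follow-up for a full-course patient. It is a larger share for a patient who stops early: 1/17 = 5.9% if the termination visit is at Week 16 and follow-up is one week later.

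**3. Whether exposure continues.** Protocol 1.4 gives a half-life of 30 to 35 days. Assuming simple exponential decline, 0.5^(7/30) = 85% to 0.5^(7/35) = 87% of the infused IgG remains at 7 days, and 72% to 76% at 14 days. The gap is not an off-drug period.

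**4. Which events can fall in the gap.**

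- *TEE.* This is the clean case. Protocol 6.1.11 requires both Wells scores at Week 33 whatever the Week 32 findings, and a DVT score of 2 or more triggers Doppler and D-dimers. A DVT or PE starting after termination is actively looked for and reported as an SAE, then falls outside the 11.1 window.
- *HTR.* This route is narrow. Protocol 7.3.5.2 requires four findings together: positive Coombs' test, hemoglobin fall of at least 2 g/dL, haptoglobin below normal, and LDH rise. Only parameters abnormal at termination are re-tested, so the Coombs' test and haptoglobin must already be abnormal at Week 32. Only the hemoglobin or LDH criterion can be newly completed at the scheduled re-test. The investigator may then date onset to Week 32 or earlier, and the event is counted under either definition.

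**5. What one event does to an arm.** With exact 95% limits, 0/39 has an upper limit of 9.0%; 1/39 is 2.6% (0.1% to 13.5%). The documents give no rate for the gap. If the chance per patient were 0.1% to 2% (an assumption), the chance of at least one such event among 39, 1 − (1 − p)^39, would be 3.8% to 54.5%.

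**6. Why post-IGIV onset should be flagged.** At the planning rates, patients eligible for rescue number 39 × 0.9 × 0.5333 = 18.7 on placebo and 39 × 0.9 × 0.1889 = 6.6 on octanorm. Rescue is optional, so these are counts of eligible patients, not of patients treated.

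**The case against.** The strongest reply is that exclusion is only one reading. SAP 11.1 also says that every reported event will be tabulated, and its bullets for TEEs and HTRs and for SAEs carry no treatment-emergent qualifier although others do. SAP 8.4 ties the end to the observation period, says only that this is usually the termination visit, and Protocol 6.2.2 pairs the planned observation period with the final examination. All of that is correct, and it is why the claim is that events may be left out. It does not remove the problem: the sentence limiting the analysis to treatment-emergent events stands in the same section, the bracket in 8.4 names Week 32 or earlier discontinuation, and the opening of SAP 11 speaks only of treatment-emergent events. The texts conflict and nothing says which prevails.

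A reader might infer that an HTR first meeting all four criteria at Week 33 is necessarily dropped. The documents do not support that, because the test is the date of onset or worsening, not the date on which the criteria are completed.

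A reader might also infer that such events disappear. They do not: TEEs and HTRs go to the IDMC in real time, SAEs are described in the study report, and every reported TEE and HTR gets a narrative. What is uncertain is the by-arm count.

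Finally, it is fair to object that an elaborate split of tables around rescue IGIV is a matter of preference. A flag is enough.

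**Conclusion.** The point holds as an inconsistency that should be settled before unblinding. The SAP has two treatment-emergent windows, and the narrower one, read naturally, puts the safety follow-up outside the analysis, contrary to SAP 3.2.2 and Protocol 9.9.

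Its size is modest: one week in 33 for a full-course patient, and 2.6 percentage points per event in an arm of 39. This rests on the nominal visit calendar, on reading 8.4 as ending at the termination visit, and on onset or worsening being dated after that visit.

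Two further inferences go too far. The documents give no HTR rate after rescue IGIV, so the number of events that 8.3 would add to either arm cannot be stated. Nor can it be said that a combined hemolysis listing is missing, because the catalogue of tables and listings is deferred to a separate document.

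**What to change.** - Put one definition in SAP 8.3 and 11.1: first onset or worsening from the start of the first infusion through the safety follow-up visit, or 14 days after the last infusion if that visit is missed.
- For TEEs, HTRs and other SAEs, extend the window to 4 weeks after the last infusion. Label the part after the follow-up visit as passively reported, since Protocol 7.3.9 does not require active follow-up.
- State that the tables in 11.1 use this window, so that the two competing sentences there agree, and say how HTR onset is dated when the criteria are completed over more than one visit.
- Leave the treatment period in SAP 8.4 unchanged for the primary endpoint.
- In the TEE/HTR and SAE tables, flag events with onset after rescue or resumed IGIV. A full split of the tables by onset period is optional.

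The cost is wording in two SAP sections and one flag. Event dates are already collected; the start date of any non-study IgG during follow-up must be available. The list of tables is still to be supplied, so the change can be made there, before the SAP is finalized and the blind is broken.

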subjects from the PP sets. This classification of protocol deviations is the joint responsibility of the clinical study manager, the study statistician, and Octapharma's responsible medical expert, and will be agreed and documented before the database is locked and the statistical analyses are performed.

Property of Octapharma. Do not copy or distribute without written permission.

8. General Issues for Statistical Analysis

The primary, confirmatory analysis will be the comparison between *octanorm* and placebo with respect to the proportion of patients with clinically important deterioration until week 32.

In addition to the confirmatory evaluation of the primary endpoint, all data collected will be listed and presented by means of descriptive statistics and comparisons between the treatment groups.

In general, statistical summaries will be presented for all patients overall and by treatment group in a side-by-side manner.

Descriptive subgroup analyses will be performed with respect to age, sex, race (if the study population is sufficiently diverse for meaningful comparisons), and region (U.S. vs. Non-U.S.); in particular the primary efficacy outcome will be presented for each of these subgroups.

Continuous, quantitative variable summaries will in general include the number of subjects with non-missing values (N), mean, standard deviation, median, minimum and maximum, 1st and 3rd quartile.

If appropriate, continuous variables may be categorized and additionally treated as ordinal variables.

Categorical, qualitative variable summaries will include the frequency and percentage of subjects who are in the particular category. In general the denominator for the percentage calculation will be based upon the total number of subjects in the analysis population unless otherwise specified.

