9.4. Measurement of Treatment Compliance

The following parameters will be listed and summarized per subject and/or per infusion cycle:

- Body weight
- Actual dose (total and per kg body weight, based on the latest available weight measurement)
- Total dose administered
- Total number of infusions administered
- Total volume of solution administered
- Number of infusions
- Infusion times
- Use of premedication
- Overall amount of product administered (only included in data listings)

Deviations from the planned treatment schedule will be summarized by counting the number of infusion sessions that deviate from the scheduled intervals by more than the allowed intervals, and by listing all cases with more than two days deviation individually.

Property of Octapharma. Do not copy or distribute without written permission.

10. Efficacy Analysis

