11.2. Local Injection Site Reactions

Local injection site reactions will be listed, and tabulated by treatment group and MedDRA preferred term for comparison of the total number of reactions, type of reaction, severity and time of occurrence (treatment week).

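### The infusional-AE rule in SAP 11.1 omits onset during the second infusion session, and affected cycles are counted without dividing by cycles given

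*SAP*

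**What the plan says.** SAP 11.1 is the only place that defines an infusional AE. It names three onset windows joined by *or*. The first applies if "the onset is during the first infusion session of a given infusion cycle". The other two are "between the two infusion sessions of the same cycle, or within 72 hours after the end of the 2nd infusion session" of that cycle. Among the key figures it then lists the incidence and number of infusional AEs, and "Number of infusion cycles with infusional AEs". No denominator is given for the last item.

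SAP 11.2 tabulates local injection site reactions by arm "for comparison of the total number of reactions, type of reaction, severity and time of occurrence (treatment week". The introduction to SAP 11 says that "data tabulations will present the treatment arms and the total count in a side-by-side manner".

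Exposure is handled separately. SAP 9.4 lists "Total number of infusions administered" among the compliance summaries, and SAP 8 says that in general "statistical summaries will be presented for all patients overall and by treatment group in a side-by-side manner". Nothing links these exposure figures to the AE counts. SAP 8 also sets the usual percentage denominator as subjects in the analysis population.

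**The concern.** **The window.** A reaction that begins during an infusion is the plainest case of an infusional AE. The rule captures it in session 1 and drops it in session 2, and every full cycle has two sessions. A programmer following the text would exclude these events from the infusional AE counts and from the affected-cycle count.

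**The denominator.** Patients who deteriorate are discontinued (SAP 4.1), and the plan expects this far more often on placebo. If octanorm works, its patients stay longer and receive more cycles. A raw count of affected cycles, or of local reactions, then tends to show an excess on octanorm even when the risk per cycle is the same. A reader of the side-by-side table could take longer treatment for worse tolerability.

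**Working it through.** **1. Can another rule catch session-2 onset?**

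| Onset | Covered by SAP 11.1? |
|---|---|
| During session 1 | Yes |
| Between sessions 1 and 2 | Yes |
| During session 2 | No |
| 0–72 h after the end of session 2 | Yes |

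The previous cycle's 72-hour window cannot fill the gap. It is tied to the same cycle, and Protocol 5.4 requires at least 4 days (96 h) between cycles. No other section defines the term. If session 2 is not given at all, the second and third windows have no anchor.

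**2. Running time omitted.** Inputs: 0.5 g/kg per week, 165 mg/mL, two sessions per cycle, at most 6 simultaneous sites, 20 to 30 mL/h per site, 180 mL/h in total (Protocol 5.1, 5.4, 5.5); 1 to 54 h between sessions (Protocol Table 5); maximum weight 120 kg (Protocol 4.1.2). Assumptions: equal split between sessions, lowest weight 50 kg, at least 3 simultaneous sites.

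- Session volume = 0.5 × weight / 0.165 / 2: 75.8 mL at 50 kg, 181.8 mL at 120 kg.
- Session time d: 75.8/180 = 0.42 h (6 sites at 30 mL/h) to 181.8/60 = 3.03 h (3 sites at 20 mL/h).
- Share of the intended window = d / (2d + gap + 72):
  - 50 kg, 180 mL/h, 54 h gap: 0.33%
  - 120 kg, 6 sites at 20 mL/h, 1 h gap: 1.99%
  - 120 kg, 3 sites at 20 mL/h, 1 h gap: 3.83%

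This is a share of time, not of events. The documents give no onset distribution.

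**3. The plan's own figures (SAP 6).**

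- Composite failure rates: 0.10 + 0.90 × 0.1889 = 27.0%; 0.10 + 0.90 × 0.5333 = 58.0%.
- Sample size, pooled variance, two-sided 5%, 80% power: [1.960 × √(2 × 0.425 × 0.575) + 0.842 × √(0.27 × 0.73 + 0.58 × 0.42)]² / 0.31² = 38.7, so 39 per arm, as stated. Power at 39 is 80.3%.

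**4. Expected cycles per patient.** A full course is 32 cycles. All failures are assumed to stop treatment. The timing of stops is not in the documents, so it is varied. If failures stop on average at week w, expected cycles are 32(1 − p) + w·p. Under a constant hazard with stops at the 4-weekly visits, they are 4 × Σ(1 − p)^(k/8) for k = 0 to 7.

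| Stop pattern | Octanorm | Placebo | Ratio |
|---|---|---|---|
| Constant hazard, 4-weekly stops | 28.00 | 22.58 | 1.24 |
| Constant hazard, continuous | 27.45 | 21.39 | 1.28 |
| Even over weeks 4–28 (mean 16) | 27.68 | 22.72 | 1.22 |
| Even over weeks 4–32 (mean 18) | 28.22 | 23.88 | 1.18 |
| All at week 4 | 24.44 | 15.76 | 1.55 |
| All at week 8 | 25.52 | 18.08 | 1.41 |
| All at week 24 | 29.84 | 27.36 | 1.09 |
| All at week 32 | 32 | 32 | 1.00 |

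**5. What the table would show.** Take 39 patients per arm, stops averaging week 16, and an assumed 10% risk per cycle in both arms. Cycles given are 39 × 27.68 = 1,080 and 39 × 22.72 = 886. The planned count is about 108 against 89 affected cycles. Divided by cycles given, it is 10% against 10%.

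**6. Can a reader rebuild the rate from SAP 9.4?** Not safely, because SAP 9.4 does not say what an infusion is. The SAP Preface uses the word for the weekly cycle ("The weekly infusion will be performed in two separate sessions"), while Protocol Table 1, footnote 4, uses it for a single session. A full course is then 32 or 64.

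**The case against.** The window gap is evidently a drafting slip: one continuous window was meant. It covers little time, applies equally to both arms and loses no event altogether. Session-2 onsets stay in the overall TEAE, related, serious, TEE/HTR and withdrawal tables, and local reactions have their own table in SAP 11.2. The 3.8% upper end needs the heaviest eligible patient and only 3 simultaneous sites, a number the protocol does not give; with 6 sites it is 2.0%.

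On the denominator, the key-figure list in SAP 11.1 is not exhaustive, the table list is deferred, and exposure is summarised by arm in SAP 9.4. Patient-level incidence is also planned, and it is not proportional to cycles given. SAP 11.2 tabulates reactions by treatment week. No passage says octanorm will receive more cycles; that is inferred. Failures also include patients with missing endpoint data and those who first deteriorate at week 32, and both narrow the difference.

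Most of this stands as a limit on size. It does not remove either problem. Intent does not change what the text tells a programmer to do. Incidence also rises with time on treatment. The treatment-week table helps only if it shows the number still on treatment each week. A deferred table list is a reason to specify the denominator now. The protocol itself quotes local reactions per infusion (0.028 to 0.697 in the meta-analysis cited in Protocol 1.5), yet no planned output is on that scale.

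**Conclusion.** Both points hold. The definition is wrong as written: it excludes onset during one of the two sessions in every full cycle. The omitted time is roughly 0.3% to 3.8% of the intended window under the assumptions above; fewer sites or slower rates would raise it, and the share of events lost cannot be estimated.

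The affected-cycle and local-reaction counts are not comparable between arms if exposure differs. At the plan's own failure rates the octanorm/placebo ratio of cycles is about 1.2, ranging from 1.00 to 1.55 with the unstated timing of stops. The direction follows from the discontinuation rule and the planning rates; the exact size is illustrative. The safety analysis is descriptive, so the primary endpoint and all tests are untouched. Both points should be corrected before the table list is finalised.

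**What to change.** - **SAP 11.1:** define an infusional AE as one with onset from the start of session 1 to 72 hours after the end of the last session given in that cycle. This closes the session-2 gap and also covers cycles in which only one session was given.
- **SAP 11.1 and 11.2:** keep the planned figures and add, by arm, affected cycles divided by cycles given, and infusional AEs and local reactions per cycle given.
- **SAP 9.4:** state whether an infusion is a cycle or a session, and use cycles as the denominator for the new rates.
- **Treatment-week table:** show the number of patients still on treatment each week.

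Rates per patient-year and confidence intervals that allow for repeated events within a patient are optional. The cost is one line of SAP wording, a clarified label and some table columns. Onset times and infusion details are already recorded, so no new data are needed.
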